- > FVIII activity levels (baseline)
- Anti-human and anti-porcine FVIII antibody titers (baseline)
- Prior treatment with hemostatic agents (baseline)
 - o Regimen received
 - Medication start/stop dates (retrospective cohort only)
- Comorbidities (baseline)
 - Physician assessment of association with AHA (possibly associated with causation of AHA/not associated with AHA)
- Current medications not related to AHA (taken within 14 days)
- ➤ AHA diagnosis
- Presentation of AHA symptoms
- Immunosuppressive agents received to treat underlying AHA during current Obizur treatment (baseline and follow-up)
- Obizur utilization (baseline and follow-up)
- Length of hospital stay per bleed (days)
- Safety (collect all SAEs; endpoint is therapy-related SAEs)
 - Key safety concerns:
 - o Inhibitor development against pFVIII (follow-up)
 - Hypersensitivity reactions including anaphylaxis
 - Thrombogenicity
 - Outcomes, including date of death
- Physician bleed cessation assessment
 - Bleeding stopped versus not stopped
 - Date bleeding stopped

- ➤ If bleeding not stopped, note reason (e.g., death, new treatment)
- FVIII activity measurements throughout treatment
- Human and porcine FVIII antibody titers. [Requirement to have a reference lab for anti-porcine FVIII antibody measurement (Central lab available if physician chooses to use it)]
- Concurrent bleeding episodes (baseline or follow-up)
 - Appearance of bleeding at a new site
- Treatment for bleeding episodes that occur greater than 72 hours after stopping treatment for the original bleed

Data sources:

Data wil be extracted from existing patient medical charts.

All prospective data shall be transcribed into the EDC system within 14 days of entry into the patient chart.

Retrospective data collection (for subjects who were treated with Obizur prior to initiation of the prospective study) will be completed within approximately 2 months of IRB approval.

Post-electronic data entry, medical dictionary for regulatory activities (MedDRA) coding will be conducted for all medical conditions reported and WHODRUG coding for all reported medications.

Study size:

There will be one cohort of approximately 40 patients with AHA who have had a bleeding episode and are being treated with Obizur. In addition, Baxalta expects there will be approximately 30 to 40 patients who were treated with Obizur prior to the initiation of the prospective study, on whom retrospective data will be collected.

Data analysis:

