6. MILESTONES

Milestone	Planned Date
Final protocol submission	31MAR2015
Start of all data collection/First site initiated	30SEP2015
Last subject in	31MAR2019
Last subject out	30SEP2019
Data lock for prospective data collection	01OCT2016
Data lock for prospective data collection	01OCT2017
Data lock for prospective data collection	01OCT2018
Data lock for prospective data collection, final report	31OCT2019
Data lock for Report on retrospective data	15DEC2015
Report on retrospective data results	30JAN2016
Annual study update report	15DEC2016
Annual study update report	15DEC2017
Annual study update report	15DEC2018
Final clinical study report	31JAN2020

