9. RESEARCH METHODS

9.1 Study Design

This study is a multi-center, uncontrolled, open-label, non-interventional postauthorization safety surveillance study to describe the use of Obizur in patients with AHA, and secondarily, where data are available, to describe the hemostatic effectiveness and immunogenicity of Obizur. Approximately 40 male and female patients ≥18 years of age with AHA in the United States will be enrolled over a 3.5 year period with follow-up from the date of treatment through 180 days; it is expected this prospective study will enroll up to two patients per month. Patients should be enrolled within five days of initiating Obizur to ensure unbiased prospective observation.

In addition, in an attempt to collect all safety and utilization data on patients treated with Obizur since Food and Drug Administration approval in October 2014, Baxalta will conduct a retrospective chart review on persons treated with Obizur prior to the prospective study start date. Baxalta expects there will be approximately 30 to 40 patients who were treated with Obizur prior to the study start date, on whom retrospective data will be collected.

Prospective data will be collected for each subject over a period of approximately 180 days from the time of Obizur treatment; in addition, data points that are retrospective in nature (such as comorbidities and prior medical treatment) will be obtained from the medical chart for the time period prior to Obizur treatment. A subject or a subject's legally authorized representative will provide signed informed consent according to local regulations, prior to data collection initiation. Signed informed consent should be obtained within five days of Obizur treatment for patients newly treated with Obizur.

Among patients in the retrospective cohort, for whom Obizur treatment occurred prior to initiation of the prospective study, signed informed consent will be obtained at the time the patient has a clinic visit. If the patient is deceased or lost to follow-up, only anonymized data will be collected from the medical chart and entered into the electronic data capture (EDC) system.

The choice of Obizur use is to be made *independent of and prior to* any decision by the subject or the subject's legally authorized representative to participate in this study. The treating physician will determine the treatment regimen, as well as frequency of laboratory and clinical assessments, according to routine clinical practice.

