9.2.2 Duration of Study Period(s) and Subject Participation

For the prospective portion of the study, the overall study enrollment and collection period will be 4 years from study initiation (i.e., first site initiated) to study completion (i.e., last subject out). The recruitment period is expected to be 3.5 years. Subject participation period is 180 days for each qualifying bleeding episode. Including start-up and closure, the entire study will take approximately 4.5 years.

Retrospective chart review will be conducted for approximately six weeks after the first site is initiated for the patients with a bleeding episode during which they were treated with Obizur prior to the start date of the prospective study. Utilization data for this group of patients will be presented in a one-time Retrospective Utilization Data Report.

Persons with a bleeding episode prior to study start date will be asked to provide written informed consent, so data can be collected for up to 180 days post-treatment. For several patients, this will require some retrospective and some prospective data collection. Subjects from both groups (prospective and retrospective) will be included in the Annual Study Update Report, and their inclusion in the overall analysis will be outlines in the statistical analysis report (SAP).

- First site initiated: September 2015
- Data lock for retrospective data collection: December 2015
- Report of retrospective utilization results: January 2016
- Last subject in: March 2019
- Last subject out: September 2019
- Final clinical study report (CSR): January 2020

Subjects who have a bleeding episode successfully controlled by Obizur may be retreated with Obizur for any subsequent bleeding episode; these subjects will not be double-counted in the total 40 patients, but will be deemed a separate bleeding episode in analysis. Subsequent bleeds are defined as bleeds that occur greater than 72 hours after finalizing initial treatment For each bleed newly treated with Obizur, the 180-day follow-up period will restart. If a subject experiences a new bleed within the ongoing 180-day follow-up period, the subject will (a) still be followed for the original 180 days and (b) will also be followed for 180 days post the 2nd bleed, or until the study ends (i.e., there will be overlap in the follow-up period).

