9.2.6 Screening and Follow-up

The study site is responsible for maintaining an enrollment/screening log that includes all subjects enrolled. The log also will serve to document the reason for screening failure or decision to not enroll. All screening data will be collected and reported in CRFs, regardless of screening outcome. If a subject is re-screened, the End of Study CRF should be completed, and a new ICF, new SIC and new CRF are required for that subject.

The overall study design is illustrated in Figure 1.

Figure 1
Study Design for Baxalta Non-Interventional Study Protocol 241302

Obizur [antihemophilic factor (recombinant), porcine sequence]
prescribed by a physician

ective data collection if treatment prior to study initiation (with ontion

- Retrospective data collection if treatment prior to study initiation (with option for follow-up duration: 180 days post-treatment); enroll at first clinic visit
- Prospective data collection (duration: 180 days) if treatment on or after study initiation; up to five days to enroll from treatment initiation

[figure not shown]

Table 1. **Schedule of Study Assessments**

		Baseline	Interval/Data available per existing patient visits, medical charts						Study
Assessments	Screening		Time A	Time B	Time C	Time D	Time E	Time F, etc.	Completion/ Termination ^a
Informed Consent b	X					0			
Eligibility Criteria ^b	X				C				
Demographic Information		X							
AHA Information		X	X	X	X	X	X	X	
Medical History		X	X	X,C	X	X	X	X	
Concomitant Medications		X	X	X	X	X	X	X	X
Safety: SAEs		X	X	X	X	X	X	X	X
Laboratories (as available) c		X	X	X	X	X	X	X	X
Obizur Treatment Information		X	CX	X	X	X	X	X	X
Concurrent Bleeding Episodes		X	X ^d	X^{d}	X^d	X^d	X ^d	X^{d}	

- a Include for cases of withdrawal or discontinuation.
 b Occurs before start of data collection.
 c For laboratory assessments, see Table 2.
 d Only if additional bleeds occur.

Table 2. Clinical Laboratory Data Collection Clinical Laboratory Data Collection									
	c ·	D II	Interv	al/Data ava	Study				
Assessments	Screening	Baseline	Time A	Time B	Time C	Time D	Time E	Time F, etc.	Completion/Terminationa
Hematology*								11	
Hemoglobin		X							
Hematocrit		X							
CBC with differential, if consistent with local practice		X							
FVIII anti-human and anti-porcine antibodies±		X							

^{*}Given the observational nature of this study, data will be collected as recorded. No laboratory assessments are mandated by this Protocol.

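### Patients treated before study start enter from the chart if dead or lost but need a routine clinic visit if alive, and no route is stated for a living patient with no visit before the retrospective review ends

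*Protocol*

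**What the plan says.** The Protocol adds a retrospective chart review to the prospective cohort, "in an attempt to collect all safety and utilization data on patients treated with Obizur since Food and Drug Administration approval" (section 9.1). It expects 30 to 40 such patients.

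Two entry routes are given.

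- **Living patients.** "signed informed consent will be obtained at the time the patient has a clinic visit" (section 9.1, repeated in the Abstract). Figure 1 in section 9.2.6 agrees: "enroll at first clinic visit". Section 9.1 also states generally that the subject or representative "will provide signed informed consent according to local regulations, prior to data collection initiation".
- **Dead or lost patients.** "If the patient is deceased or lost to follow-up, only anonymized data will be collected from the medical chart" (section 9.1, repeated in section 9.2.4).

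Section 9.1 also says that the study requires no visits, so routine care alone decides whether a living patient is seen.

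The collection period is described in three ways.

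- Section 9.2.2: "Retrospective chart review will be conducted for approximately six weeks after the first site is initiated".
- Abstract, Data sources: retrospective collection "will be completed within approximately 2 months of IRB approval".
- Section 6: "Start of all data collection/First site initiated 30SEP2015", with the lock for the retrospective report on 15 December 2015 and the report itself on 30 January 2016.

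Section 9.2.2 describes that report as a single utilization report. It also places both groups in the annual updates and leaves the handling of the retrospective group in the overall analysis to the SAP.

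**The concern.** Whether a patient treated before study start is counted depends on what happened to that patient. A death is captured from the chart. A survivor is captured only by coming to clinic and signing. A patient treated in late 2014 who has recovered may have no reason to attend in autumn 2015. If that patient is not classed as lost, no stated route brings the record in.

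The denominator then loses living patients while the numerator keeps every death, so the death proportion is too high. Lost patients are over-represented in the same way. The doses and infusion counts in the retrospective report would describe that distorted mix. If entry is not kept open, the same mix passes into the annual updates and into any pooled analysis; section 9.5 considers raising the evaluable number from 40 to 50 with retrospective patients. An SAP cannot repair this, because patients who never enter leave no data.

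**Working it through.** **Plan's own figures.** The Protocol gives no figure for how completely the retrospective group will be captured. Its only precision figures are the exact intervals in section 9.5. They reproduce (5% of 40: 0.6% to 16.9%) and are not in dispute.

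**Inputs from the Protocol**

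- Windows: six weeks = 42 days (9.2.2); two months, about 61 days (Abstract); 30 September to 15 December 2015 = 31 + 30 + 15 = 76 days (section 6).
- Expected patients: 30 to 40 (9.1); 35 is used here.
- Mortality: 3% to 22% (section 7.1). This is mortality due to bleeding only; no all-cause figure is given.

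**Assumptions**

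- The true dead-or-lost share is D = 20%.
- Living patients attend at even intervals (1, 3 or 6 months; 3 months = 91 days, 6 months = 182 days).
- All living attenders consent.
- All dead and lost patients are found and entered.
- Entry stops at the end of the window.

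**Formulas**

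- Share of living patients captured: v = min(1, window / visit interval).
- Observed dead-or-lost share: D / [D + (1 − D)v].
- Records from 35 treated: 35 × [D + (1 − D)v].

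**Results for D = 20%**

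| Visit interval | Window (days) | v | Observed share | Records of 35 |
|---|---|---|---|---|
| 3 months | 42 | 42/91 = 0.46 | 35% | 19.9 |
| 3 months | 61 | 61/91 = 0.67 | 27% | 25.8 |
| 3 months | 76 | 76/91 = 0.84 | 23% | 30.4 |
| 6 months | 42 | 42/182 = 0.23 | 52% | 13.5 |
| 6 months | 61 | 61/182 = 0.34 | 43% | 16.4 |
| 6 months | 76 | 76/182 = 0.42 | 37% | 18.7 |
| 1 month | any | 1 | 20% | 35 |

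For the first row: 0.20 / (0.20 + 0.80 × 0.46) = 0.35.

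**Deaths alone, over the Protocol's mortality range.** With no lost patients and v = 0.46, a true 3% reads 0.03 / (0.03 + 0.97 × 0.46) = 6.3%, and a true 22% reads 0.22 / (0.22 + 0.78 × 0.46) = 38.0%. With v = 0.69 (a 42-day window and 2-monthly visits) they read 4.3% and 29.0%. If 10% are also lost and v = 0.46, a true 22% reads 34.8%, and the lost share rises from 10% to 15.8%.

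**Direction.** The observed share exceeds D whenever v is below 1, through missing visits or declined consent, and equals D when v = 1. The 76-day figures are the most lenient reading: all windows except the Abstract's run from the first site, so a site that opens later has less time.

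**The case against.** The strongest reply is that nothing in the Protocol closes entry at the end of the review. In section 9.2.2 the six weeks describe the chart review that feeds the one-time report. The next paragraph says that patients with an earlier bleed will be asked for written consent, names no deadline or visit, foresees some prospective collection up to 180 days after treatment, and places both groups in the annual updates. Figure 1 sets no closing date. This stands: a reader might infer that a living patient not seen within six weeks to two months is permanently excluded, but the text does not say so. It does not say the opposite either. The Abstract gives a completion time for retrospective collection, and section 9.2.2 lists a December 2015 lock for it. The one-time report is exposed on either reading.

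Second, loss to follow-up is defined in section 9.2.7 only for study subjects. A site could class a recovered non-attender as lost and enter the chart data, and most of the distortion would then vanish. That is also correct, but it leaves each site to decide who enters.

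Third, a reader might infer that SAEs, inhibitors and failed bleed control are inflated as well. The calculation does not show this. Lost patients have truncated charts, which can lower recorded events. Nor is it established that 30 to 40 patients cannot be reached: with 76 days and 3-monthly visits, about 30 of 35 enter.

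Finally, the planned primary cohort is the 40 prospective patients. Pooling is conditional and left to the SAP. Sites already keep a log with reasons for not enrolling (section 9.2.6), although it is not clear that this covers treated patients who were never approached.

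**Conclusion.** The point holds as an unequal and incompletely specified entry rule, set against an aim of complete capture. Entry depends on vital status and attendance; one group, alive, not lost and unseen, has no stated route; the period has two descriptions that do not match; and the key term is undefined for this cohort.

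The direction is firm for deaths and for lost patients whenever some living patients do not attend and consent in time. The size is not known. From an assumed 20%, the observed share ranges from no change with monthly visits to 52% with 6-monthly visits and a 42-day window. Visit interval, consent rate and the true share are all assumptions, and the larger figures require entry to stop with the window. Effects on SAEs, inhibitors and bleed control are possible but not shown. The primary result is touched only if the cohorts are pooled. The change is worth making because it is cheap and cannot be made at the analysis stage.

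**What to change.** In sections 9.1 and 9.2.2 and Figure 1, with the Abstract aligned:

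1. Reconcile the six-week and two-month descriptions of the review.
2. State that entry of retrospective patients stays open through the annual data locks, with the 15 December 2015 lock as a first cut.
3. Allow consent by mail or telephone, without waiting for a clinic visit, where the IRB accepts it.
4. Define loss to follow-up for patients who were never enrolled.
5. Report, per site, the number of treated patients from pharmacy dispensing records (already source data in section 9.4.1) against the number entered, by vital status. This also shows any imbalance that remains because living patients can decline consent.

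The cost is protocol and consent-form wording and IRB agreement to remote consent. The January 2016 report becomes provisional and is completed in the annual updates, which already include both groups. No visit or test is added, so the study stays non-interventional.

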9.1.1 Primary Outcome

The primary outcome is patient safety in terms of AEs, their seriousness and severity. In particular, describing:

• Incidence of therapy-related SAEs and level of severity

9.1.2 Secondary Outcomes

Secondary outcomes will describe:

- Effectiveness assessment for resolution of bleeding, determined as either bleeding stopped or didn't stop
 - ➤ If bleeding did not stop, a reason should be provided (e.g., death)
- Time to bleeding resolution, death, or switch to another treatment.
- Number of Obizur units/kg required for control of bleeding (bleeding stopped)
- Number of Obizur infusions required for control of bleeding (bleeding stopped)
- Newly recognised anti-pFVIII inhibitors or increase in titer of anti-pFVIII
 inhibitors from pre-treatment level, impact on hemostatic efficacy and associated
 clinical manifestations if any, and evolution of titer over time
- Occurrence of hypersensitivity reactions
- Occurrence of any thrombogenic event

9.2 Setting

9.2.1 Medicinal Product(s)/Medical Device(s)

Administration, packaging, labeling, and storage for the product are described in the product labeling.

The active ingredient in Obizur is a recombinant analogue of porcine factor VIII (pFVIII) with an approximate molecular weight of 170 kDa. The rpFVIII molecule in Obizur is a glycoprotein containing a 90 kDa heavy chain and a 80 kDa light chain. The B-domain normally present in naturally occurring pFVIII has been replaced with a twenty-four amino acid linker. Once activated, the resulting rpFVIIIa has a comparable activity to the endogenous human FVIIIa.

Obizur is expressed in a genetically engineered baby hamster kidney (BHK) cell line which secretes rpFVIII into the cell culture medium, and the rpFVIII protein is then purified using a series of chromatography and filtration steps. The production process includes two dedicated viral clearance steps - a solvent/detergent treatment step for viral inactivation and a nanofiltration step through a series of two 15-nm filters for removal of viruses. No additives of human or animal origin are used in the formulation of Obizur.

Obizur is formulated as a sterile, non-pyrogenic, lyophilized powder for intravenous injection after reconstitution with the diluent (Sterile Water for Injection). Obizur is available in single-use vials that nominally contain 500 units (U) per vial. When reconstituted with the diluent, the product contains the following components per mL: 8.8 mg sodium chloride, 0.04 mg Tris-base, 0.73 mg Tris-HCl, 1.47 mg tri-sodium citrate dehydrate, 0.15 mg calcium chloride dehydrate, 1.9 mg sucrose, and 0.05 mg polysorbate 80.

Each vial of Obizur is labeled with the actual rpFVIII activity expressed in U determined by a one-stage clotting assay, using a reference rpFVIII material calibrated against the World Health Organization (WHO) 8th International Standard for human FVIII concentrates. The specific activity of Obizur is in the range of 11000 - 18000 U per milligram of protein. The potency values of Obizur determined by the chromogenic assay vary and are approximately 20-50% lower than those of the one-stage clotting assay.

9.2.2 Duration of Study Period(s) and Subject Participation

For the prospective portion of the study, the overall study enrollment and collection period will be 4 years from study initiation (i.e., first site initiated) to study completion (i.e., last subject out). The recruitment period is expected to be 3.5 years. Subject participation period is 180 days for each qualifying bleeding episode. Including start-up and closure, the entire study will take approximately 4.5 years.

Retrospective chart review will be conducted for approximately six weeks after the first site is initiated for the patients with a bleeding episode during which they were treated with Obizur prior to the start date of the prospective study. Utilization data for this group of patients will be presented in a one-time Retrospective Utilization Data Report.

Persons with a bleeding episode prior to study start date will be asked to provide written informed consent, so data can be collected for up to 180 days post-treatment. For several patients, this will require some retrospective and some prospective data collection. Subjects from both groups (prospective and retrospective) will be included in the Annual Study Update Report, and their inclusion in the overall analysis will be outlines in the statistical analysis report (SAP).

- First site initiated: September 2015
- Data lock for retrospective data collection: December 2015
- Report of retrospective utilization results: January 2016
- Last subject in: March 2019
- Last subject out: September 2019
- Final clinical study report (CSR): January 2020

Subjects who have a bleeding episode successfully controlled by Obizur may be retreated with Obizur for any subsequent bleeding episode; these subjects will not be double-counted in the total 40 patients, but will be deemed a separate bleeding episode in analysis. Subsequent bleeds are defined as bleeds that occur greater than 72 hours after finalizing initial treatment For each bleed newly treated with Obizur, the 180-day follow-up period will restart. If a subject experiences a new bleed within the ongoing 180-day follow-up period, the subject will (a) still be followed for the original 180 days and (b) will also be followed for 180 days post the 2nd bleed, or until the study ends (i.e., there will be overlap in the follow-up period).

